Evaluating the Efficacy of Lateral Heel Wedges for Osteoarthritis of the Knee

NCT: 02254473 March 1, 2014

Evaluating the Efficacy of Lateral Heel Wedges for Osteoarthritis of the Knee

Principal Investigator: [name]

Significance

Given the prevalence of osteoarthritis of the knee and the general aging trends of the population it is important to develop effective non-operative interventions to reduce pain and improve function in the adult population with osteoarthritis (OA) of the knee. A large body of experimental evidence documents the potential for cartilage regeneration in the osteoarthritic joint under conditions of mechanical unloading of the involved joint. An easily applied, off-the-shelf shoe insert material that, when configured properly, will unload the medial compartment of the knee has been developed. The purpose of this investigation is to document the acceptability and effectiveness (with patient reported measures) of this insert compared to a control insert which does not unload the medial compartment of the knee in a group of patients with significant OA of the medial compartment of the knee in order to develop pilot data to document the effect size, acceptability of the inserts, compliance, feasibility, and power for a future clinical trial. Following communication with NIAMS officials we plan to submit an R34 proposal for this purpose. Multiple clinical trials measuring the impact of shoe inserts on knee OA symptoms report minimal benefit. These trials are conducted in a manner which used: 1. self-reported OA, 2. subjects not presenting for treatment and 3. Not in a stratified population of patients with moderate to severe medial compartment OA. Our study selects for patients with this moderate to severe medial compartment OA who pass the screening test of sufficient MCL laxity to allow correction of the weight bearing axis. Further the material used in these inserts is of a different stiffness which is molded to that of the human heel pad. This clinical trial will likely never be industry funded because of the inexpensive nature of the intervention.

Objectives and Hypothesis

Regularly wearing a 5 degree sloped insole over the course of one year will result in a wider joint space by x-ray in 60% of the subjects, a significant decrease in knee pain, decreased use of over the counter analgesics, and a clinically important 2 point improvement in the Womac pain and stiffness scale.

Methods

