This group would otherwise be candidates for surgical intervention. Those with end stage osteoarthritic lesion would have biological potential for restoration of the cartilage. They would have range of motion that provided near normal gait and flexion enough to rise out of a chair. The insole fitting would accommodate the candidate's foot anatomy, any pathology and the geometry of their shoe.

Rationale for exclusion:

This criterion removes those conditions that would have potential to add conflicting data to the study and/or produce discomfort for the subject.

Statistical analysis plan:

All analyses will be done using S.A.S. (version 9.2) and two-sided p-values of less than 0.05 will be considered statistically significant. Appropriate descriptive summary statistics (including means and s.d.) and graphs (including histograms, kernel smoothed density plots, error bar plots) will be utilized to summarize Womac pain, stiffness and function in each treatment group at baseline, 6 month visit and 12 month visit. We will consider a linear regression using the generalized estimating equation (gee) approach to estimate the Womac pain, stiffness and function differences between wedge insert and flat insert groups with intention-to-treat principle. We selected gee as the primary approach as it accounts for the potential correlations among repeated measures within subjects. In addition, it has been shown the gee is more efficient compared to the two sample t-test, the paired t-test, the analysis of covariance (including treatment and baseline response as covariates), and is asymptotically equivalent to the analysis of covariance ii (including treatment, baseline response and an interaction between treatment and baseline response as covariates) 40. Missing data will be handled with multiple imputation using S.A.S. proc mi and mianalyze. Secondary outcomes will include clinical and functional outcomes with standardized knee radiographs, a validated University of Minnesota pain and acceptability scale, a medication log in terms of weekly hours of insert usage will be analyzed similarly and the Tegner Activity Scale to document any change in activity level in addition to the function addressed in the other outcomes instruments

Test Intervention:

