The Insoles: A commercially available proprietary insole in the form of a slab 10.5 cm wide and 35.5 cm. long will be used. They are available in two geometries and materials. The control insole is blue in color with a thin felt cover to be next to the subject's skin. It is 3 mm level depth side to side and front to back. The material is a proprietary material known commercially as Poron® with a durometer of 25; the average durometer of the human foot is 25-35 depending upon the thickness of the plantar soft tissue and the presence of bone beneath.

The experimental insole is a slab is green in color and made of polyvinyl acetate with a felt layer opposite the patients skin. It has a 5 degree wedge and is 3 mm high on thin side and 10 mm high on the other side. This insole will be fitted with the pattern cut so the outer side of the foot would have the maximum depth of material (the highest side).

Study Procedures:

Patient related: We will recruit 80 subjects presenting for treatment of knee who have primary OA of the knee primarily involving the medial compartment and meet the inclusion criteria. The will be randomized via a random table generated computer program to the wedge inserts or the flat inserts. They will be screened for adequate knee laxity and subtalar motion before enrollment at each site.

Subjects, experimental and control, will complete the Womac based on their current function, have bilateral standing knee radiographs obtained in a standardized fashion and be fit with the inserts and instructed to return in 6 weeks to have new inserts fashioned. The patient contact will be performed by the clinical coordinator. At the 6-week visit, the patients randomized to the wedge insole will have the 5 degrees insoles fit after their 6-week adjustment period with the 2.5 degrees insoles while those in the control group will be fit with new inserts.

At 3, 6, 9 and 12 months, all patients will return for new inserts and to complete secondary radiographs (6 months only) and to turn in their shoe insert acceptability, use logs and medication logs. Patients will be supplied with as many inserts as they need to assure that the shoes they wear on a daily basis are included.

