At 1 year, a convenience sample of 5 patients in the wedge (treatment) group and 5 patients in the control group who have had prior knee MRI's within 1 year of institution of the treatment shoe inserts will have knee MRI's repeated to check the quality of medial compartment articular cartilage.

Statistical Analysis

The data analysis will be done in a blinded fashion by our statistician. The Womac and Tegner data will be analyzed with standard statistical approaches and confounding variables of medication use and time of use of the shoe inserts will be analyzed with regression techniques. Knee medial compartment width will be measured by two blinded radiologists.

Subject Instructions: Subjects will be informed they are eligible to be part of a study testing various insoles of differing color, material and shape for their impact on arthritic knee pain and function. They will be instructed on insertion and removal of the insoles including printed material of such instructions. After a 6 week run in period utilizing the 2.5 degree lateral wedge test article in order to adjust to the altered weight bearing axis, the subjects will have a 5 degree wedge test article fashioned in the same manner. They will be instructed to return at 3 month intervals for fitting of new insoles and clinical evaluation. X-rays , medication logs, U of MN pain scale¹, Tegner and Womac will be collected at enrollment, 6 weeks, 3 months, 6 months, 9 months and one year.

Tailoring the Insole:

An exam will be performed ensuring the subjects foot and ankle range of motion.

The existing insoles will be removed from both shoes. This method provides maximum toe box height. It also makes a more uniform insole material bilaterally thereby providing consistency. In both groups the insole will be tailored to the subject's anatomy, pathology, and existing shoe geometry. The subjects will be fitted with the tailored insole that extends from the back of the heel to just beyond the metatarsal head, thereby maximizing room in the toe box. Multiple tailoring may be necessary to achieve comfort. The subjects are instructed on the ease of removing and placing the insole so they can move them shoe to shoe, day to day. The insoles will be replaced every 3 months. The Study Coordinator at the local site will have printed instructions to facilitate and perform the fitting of the test and control inserts based on patient randomization.

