Our podiatry consultant will be involved with the training of the research coordinator for patient screening for adequate knee medial laxity and subtalar motion as well as proper fitting of the inserts. He will be the primary contact for questions during the trial related to insert fit. We will hold a one day meeting at TRIA Orthopaedic Center in Minneapolis for the site investigator to review study procedures emphasizing patient screening and consent, procedures for standardizing radiographs, and the technique for application of the shoe inserts and procedures for managing drop out of patients.

Procedures for standardization of subject screening and recruitment, application of test and control inserts; radiographic measure will be done at a one day meeting for the staff at TRIA Orthopaedic Center. The details of the administration of the U of MN pain scale, shoe insert use log, insert acceptability scale, medication log, Tegner and Womac will be reviewed.

With approval from NIAMS officials, we intend to follow this proposal with an R34 submission in order to plan the definitive clinical trial using the data from this proposal to develop a detailed Manual of Operations, calculate the subject numbers we will need to recruit, the estimated number of subjects we might lose to the one year follow-up requirement, the number of additional clinical sites needed to recruit the cohort within a 6 month period, and develop statistical approaches to manage confounding variables such as patient BMI, activity levels, and medical comorbidity.

Table 2:

	Initial visit (Randomization)	6 week	3 month visit	6 month visit	9 month visit	12 month visit
WOMAC, Tegner, and Pain scale	S	S	S	S	S	S
Standing AP bilateral	Р	Х	X	S	Х	Х
Lateral Affected knee	Р	Х	X	S	Х	Х
Medication log	Х	S	S	S	S	S
Shoe insert log	Х	S	S	S	S	S
Clinic visit	Р	S	S	Р	S	Р
MRI						S

P = patient expense; S = study expense; X = not done

Benefits of this intervention and study design:

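### The visit schedules disagree on whether analgesic use is recorded before treatment, and under Table 2 it is not

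*Combined protocol and SAP*

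**What the plan says.** Reduced analgesic use is one of four results predicted in Objectives and Hypothesis: "decreased use of over the counter analgesics". The others are wider joint space, less knee pain and a WOMAC improvement.

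Three places bear on when medication use is recorded:

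- **Subject Instructions** gives a single list for all visits, starting at enrollment: "X-rays , medication logs, U of MN pain scale¹, Tegner and Womac will be collected at enrollment, 6 weeks, 3 months", then 6, 9 and 12 months.
- **Table 2** has X for the medication log at the initial (randomisation) visit and S at 6 weeks and 3, 6, 9 and 12 months. The legend reads "P = patient expense; S = study expense; X = not done".
- **Study Procedures (Patient related)** opens its baseline list with "Subjects, experimental and control, will complete the Womac based on their current function", followed by radiographs and insert fitting. It names no medication log there, and has logs handed in at 3, 6, 9 and 12 months.

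Two places describe how the data are used. The Statistical analysis plan lists the log among the secondary outcomes: "a medication log in terms of weekly hours of insert usage will be analyzed similarly". The later Statistical Analysis section says that "confounding variables of medication use and time of use of the shoe inserts will be analyzed with regression techniques".

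**The concern.** A predicted decrease suggests a starting value. Under Table 2 the first log comes at 6 weeks and covers time already spent on inserts, so change within a patient cannot be estimated. WOMAC, Tegner and the pain scale are all marked as done at the initial visit. The insert log is also X there, but it can have no pre-treatment value. Among the patient-reported measures in Table 2 that do have a pre-treatment state, medication use is the only one without a baseline.

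Three further things depend on that baseline:

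- **The analysis rationale.** The Statistical analysis plan favours GEE partly for its efficiency relative to analyses of covariance that use the baseline response, and extends the same approach to the log. Without a baseline log, that argument does not carry over.
- **The covariate.** If medication use is entered as a confounder and every value is post-randomisation, the adjustment uses something the insert may already have changed.
- **The pilot's purpose.** The study is meant to supply effect size and power for a definitive trial. Without a baseline it cannot supply the baseline-to-follow-up correlation for this outcome.

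Once inserts are fitted, use can no longer be recorded before treatment.

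**Working it through.** **Step 1: the schedules side by side for the medication log.**

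| Source | Initial visit | 6 weeks | 3, 6, 9, 12 months | Collections |
|---|---|---|---|---|
| Subject Instructions | yes | yes | yes | 6 |
| Table 2 | not done | yes | yes | 5 |
| Study Procedures | not named | not named | yes | 4 |

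The Table 2 row is intact, with six entries for six visits, so this is not a fault of text extraction. Subject Instructions and Table 2 contradict each other directly at the initial visit. The baseline list in Study Procedures does not decide between them, because it also omits Tegner and the pain scale, which both other sources place at the initial visit. The plan states no figure on this point, so there is none to reproduce.

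**Step 2: precision given up if no baseline is taken.** The document gives no correlation for analgesic use, so r, the correlation between baseline and follow-up, is assumed. For one follow-up log, adjustment cuts the variance of the between-arm difference by r² and narrows the confidence interval by 1 − √(1 − r²). If the recalled baseline has reliability 0.7 (assumed), the variance cut becomes 0.7r².

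| r (assumed) | Variance cut, r² | Interval narrower by | Variance cut, reliability 0.7 |
|---|---|---|---|
| 0.3 | 0.09 | 0.046 | 0.063 |
| 0.5 | 0.25 | 0.134 | 0.175 |
| 0.7 | 0.49 | 0.286 | 0.343 |

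**Step 3: the mean of the five follow-up logs in Table 2, at r = 0.5.** The cut is cov²/var, where cov is the covariance of the baseline with the mean of the five logs, var is the variance of that mean, and each log has unit variance.

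- Equal correlation at all visits: kr²/(1 + (k − 1)r) = 5 × 0.25/(1 + 4 × 0.5) = 1.25/3 = 0.417.
- Correlation decaying by visit number, r^|i−j|:
  - cov = (0.5 + 0.25 + 0.125 + 0.0625 + 0.03125)/5 = 0.19375
  - var = [5 + 2(4 × 0.5 + 3 × 0.25 + 2 × 0.125 + 0.0625)]/25 = 11.125/25 = 0.445
  - cut = 0.19375²/0.445 = 0.084

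**Step 4: chance imbalance at the start.** The 80 patients are assumed to split 40 and 40; the allocation ratio is not stated. The standard error of the baseline mean difference is √(2/40) = 0.224 SD. A gap of 0.3 SD is 0.3/0.224 = 1.342 standard errors, so P(|difference| ≥ 0.3 SD) = 2 × (1 − Φ(1.342)) = 0.18.

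**The case against.** The strongest reply is that Table 2 is deliberate and Subject Instructions is loosely written. The Subject Instructions sentence also lists X-rays at every visit, whereas Table 2 has them only at the initial visit and 6 months, and Study Procedures limits follow-up films to 6 months. The handing-in of logs in Study Procedures also fits a diary issued at the first visit and returned later. This reading is plausible. It makes it more likely that no baseline is taken, so it strengthens the case for a change.

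A second reply is that little is lost. The treatment effect is the difference between arms, which randomisation protects without a baseline. Chance imbalance is already reflected in the standard error and is not bias. The outcome is secondary, in a pilot. All of this stands, with the usual caution about dropout, which the plan anticipates. It limits the consequence to precision, within-patient change and the balance check.

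A third reply is that the magnitudes rest on assumed correlations and cover a wide range. That is also fair. The decay model treats unequally spaced visits as equally spaced, the planned GEE is not a mean of five logs, and the 18% would apply to any roughly normal baseline variable at this sample size. The figures are illustrative.

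Finally, adjusting for post-randomisation medication use is partly a separate matter. A baseline log cures it only if the analysis sentence is changed too, and insert wear time, named in the same sentence, is post-randomisation on any schedule.

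**Conclusion.** The concern holds. The document contradicts itself on whether medication use is recorded at the initial visit, does not say which schedule governs, and provides no other record of pre-treatment analgesic use.

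Under Table 2 the trial can still compare analgesic use between arms. It cannot show within-patient decrease, adjust for starting use, see whether the arms started alike, or offer a pre-randomisation medication value as a covariate.

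The precision at stake could be small or large. At r = 0.5 alone, the variance cut is 8% or 42% for the mean of five logs, depending on how the correlation falls off. These results rest on the assumed correlations, the assumed reliability of recall and an assumed equal split of 80 patients. The contradiction itself rests on none of them.

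The point should be fixed, though it does not threaten the trial's main comparison. A related gap remains on either schedule: the Statistical analysis plan describes the log only by hours of insert wear, so how analgesic use is recorded, at baseline or later, is not stated.

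**What to change.** 1. Reconcile Subject Instructions, Study Procedures and Table 2 on when the medication log is taken, including at 6 weeks, where Study Procedures also differs from the other two.
2. Change the Table 2 initial-visit entry for the log to collected. Use the follow-up form, with a look-back period defined in the protocol, completed before randomisation and insert fitting.
3. State in the Statistical analysis plan how analgesic use is derived from the log, separately from insert wear, and that the between-arm comparison is adjusted for the baseline value.
4. State in the Statistical Analysis section whether the medication covariate is that baseline value.

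The cost is one extra form at a visit that already takes place, a table correction and a few sentences. The drawback is that baseline use is recalled while later use is logged prospectively. The baseline will be noisier and the gain in precision smaller, as the reliability column in the working shows.

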We will recruit 80 adults with Kellgren-Lawrence changes between grade 2-4 medial compartment osteoarthritis of the knee from the TRIA Orthopaedic Center in Minneapolis, MN. The subjects will be randomized to a 5 degrees lateral wedge shoe insert or a flat shoe insert of similar properties through a random table generator application which will be coordinated through the TRIA Orthopaedic Center.

Inclusion Criteria:

- Adult patients 30 years or older with symptomatic medial compartment knee osteoarthritis and Grade 2-4 Kellgren-Lawrence radiographic changes presenting for treatment of knee pain.
- Range of motion knee-flexion beyond 100 degrees and not lacking more than 15 degrees of extension.
- Subtalar and forefoot motion permitting foot/ankle eversion with weight bearing.
- Sufficient shoe toe box height to allow space for the insole and therefore comfort and compliance.
- Passive laxity of medial capsule and collateral ligament by knee extension test.

Exclusion Criteria:

- All other forms of knee arthritis other than osteoarthritis.
- Bilateral symptomatic osteoarthritis of the knee.
- Knee Instability- medial pseudo-opening of greater than grade 1 or detectable anterior-posterior instability.
- Less than Grade 2 Kellgren-Lawrence radiographic changes in the medial compartment of the knee.
- Kellgren-Lawrence radiographic changes that are greater than or equal to the medial compartment in either the patellofemoral or lateral compartment.
- Inadequate knee range of motion as demonstrated on exam.
- Balance problems requiring the use of a walker or wheel chair (ambulation with aid).
- Diabetes with peripheral neuropathy.
- History of knee arthroscopy on the index knee within the past three months of study enrollment.
- History of reconstructive (ligamentous etc.) knee surgery within one year of enrollment.
- Intra-articular steroid injection or visco supplementation on the index knee within 1 month of study enrollment.
- Stiff subtalar or forefoot joints as demonstrated on clinical exam.
- Inadequate shoe toe box depth to accommodate the shoe insoles.
- Charcot joint.
- Fixed contracture of the medial capsule and/or collateral ligament as demonstrated on clinical exam.

Rationale for Inclusion:

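### The control insert is described as similar to the wedge but differs in material, felt side, colour and thickness, so a result cannot be credited to the wedge angle alone

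*Combined protocol and SAP*

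**What the plan says.** In the combined protocol and SAP, the Methods section allocates 80 adults to a 5 degree lateral wedge or "a flat shoe insert of similar properties".

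The Insoles paragraph under Test Intervention introduces the products with "They are available in two geometries and materials". Of the control it says "The control insole is blue in color with a thin felt cover to be next to the subject's skin" and "It is 3 mm level depth side to side and front to back", and it names the material as "known commercially as Poron® with a durometer of 25". The wedge is "green in color and made of polyvinyl acetate with a felt layer opposite the patients skin", with edges of 3 mm and 10 mm. No durometer is given for it. The Subject Instructions tell participants openly that the insoles vary in colour, shape and material.

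Three other places bear on how this should be read:

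- Significance states the aim as comparing the insert with a control that does not unload the medial compartment. It also says that "the material used in these inserts is of a different stiffness which is molded to that of the human heel pad", in a paragraph that sets this study apart from earlier trials with little benefit.
- Objectives and Hypothesis attributes the expected benefit to wearing an insole with a 5 degree slope.
- The Statistical analysis plan estimates WOMAC differences between the wedge and flat insert groups.

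**The concern.** The hypothesis is about slope and the intended contrast is unloading versus no unloading. For a two-arm trial to answer that, the control should match the active insert in everything except slope, and the Methods wording suggests that it does. The Insoles paragraph shows that it does not.

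The protocol does not treat material as inert. Significance cites stiffness as a distinguishing feature of these inserts. The section on benefits of the intervention lists hardness and shape recovery among the strengths, and says that three-monthly replacement protects the material's properties. The existing insoles are taken out of both shoes to remove a source of variation, yet material then differs completely by arm.

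At stake is what the trial may conclude. A cushioning or contact effect could be reported as a wedge effect, or could hide one. The pilot's effect size is also meant to support the R34 application and to size the definitive trial. It will be the effect of this pair of products, and will not carry over to a trial with a different control material.

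**Working it through.** **Attribute comparison** (all entries from The Insoles, under Test Intervention):

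| Attribute | Control | Wedge | Tied to slope? |
|---|---|---|---|
| Material | Poron | polyvinyl acetate | no |
| Durometer | 25 | not stated | unknown |
| Felt | next to the skin | opposite the skin | no |
| Colour | blue | green | no |
| Thickness, uncut slab | 3 mm level | 3 to 10 mm | partly |

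Material, felt side and colour differ for reasons unrelated to geometry. The felt wording for the wedge is slightly ambiguous, but set against the control's wording it reads as the other face. Colour is not a mechanical difference. It matters because WOMAC is self-reported and the insoles can be told apart.

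**Thickness.** Mean wedge thickness = (3 + 10)/2 = 6.5 mm, against 3 mm, a ratio of 6.5/3 ≈ 2.2. A wedge with a 3 mm thin edge must be thicker on average than a 3 mm sheet, so part of this is unavoidable with that control. A level control of about 6.5 mm would remove the difference in mean thickness. These figures describe the uncut slab. Inserts are cut to a pattern, and no dimensions are given for the 2.5 degree insert used in the first six weeks, so the thickness actually worn is not known.

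**Can the analysis separate the two?** Write the difference between arms as D = s + m, where s is the slope effect and m is the effect of everything else that differs. Two arms give one contrast, D, for two unknowns. In a regression the slope indicator and the material indicator are the same column. GEE, intention-to-treat and multiple imputation do not change that. Nor does the planned regression on medication use and wear time, because material does not vary within an arm. The documents contain no flat control in the wedge material and no evidence that the materials are equivalent.

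**Hypothetical size.** The documents give no material effect, so this is illustration only. Assume 40 per arm (the protocol gives 80 in total and no allocation ratio), no dropout, a simple two-group comparison, two-sided 0.05, and no slope effect. For a material shift of d standard deviations, the chance of a significant result in the direction of the shift is Φ(d√(40/2) − 1.96):

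- d = 0.2: 0.2 × √20 = 0.894; Φ(−1.066) ≈ 0.14
- d = 0.4: 0.4 × √20 = 1.789; Φ(−0.171) ≈ 0.43

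The opposite tail adds about 0.002 or less. With no effect of any kind, the two-sided rate is 0.05. The sign of m is unknown. If m = −0.4 and s = +0.4, then D = 0, and a real slope benefit would be detected only at the 5% level.

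**The case against.** The strongest reply is that this is a pilot comparing two products. Significance speaks of one insert against another, the analysis compares wedge and flat groups, and the differences are disclosed both in The Insoles and to participants. On this view the only defect is one loose phrase. Much of that stands: the between-arm comparison is randomized and valid, and choosing a different control material is not in itself an error. It does not dispose of the point, because the stated hypothesis names the slope and the stated contrast is unloading.

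A reader might infer that the arms are shown to differ in stiffness. The documents do not support that. The sentence in Significance refers to the inserts collectively and contrasts them with earlier trials, not with each other. The benefits section says the durometer is known, but a value appears only for the control. Two polymer names do not establish different cushioning, and the phrase in Methods might have been meant to refer to hardness. The supportable statement is that similarity of stiffness is undocumented.

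A reader might also assume that a material effect would inflate the wedge result. The control, at 25, is the only insert documented as lying within the 25 to 35 range quoted for the human foot, so a material effect could equally favour the control.

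**Conclusion.** The point holds in a limited form. The Methods description of the control is not supported by the product descriptions: material, felt side and colour differ, thickness differs in part beyond what a wedge requires, and comparable stiffness cannot be checked. Slope and material are fully confounded, so neither a difference nor a lack of one can be attributed to wedge angle or unloading alone.

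It would be too strong to say that nothing can be credited to the wedge, or that the trial is invalid. Slope may account for all, part or none of an observed difference, and the whole-product comparison stands. It would also be wrong to present 14% to 43% as this trial's false-positive rate. Those figures follow only from an assumed material effect of 0.2 to 0.4 SD, 40 per arm and no dropout, and the conclusion does not depend on them. The size and direction of any material effect are unknown.

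**What to change.** 1. Delete the similarity phrase from Methods and describe the control as it is: a flat 3 mm Poron insert.
2. State the wedge insole's durometer beside the control's. The protocol says it is known, so this needs only a line of text. If the values are close, concern about stiffness narrows, though material, felt side and colour remain unmatched.
3. Word the hypothesis and conclusion as the wedge product versus the flat Poron product, without attributing the result to slope or unloading alone. Carry the same wording into the effect size used for the R34 application.
4. If the supplier can provide it, use instead a level control of the same material, colour and felt side, with comparable mean thickness (about 6.5 mm on the stated slab edges). This would let the result speak much more directly to slope.

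Items 1 to 3 are text changes, and their price is a narrower conclusion. Item 4 depends on availability: the documents describe a proprietary product in two geometries and materials and do not say that a level slab in the wedge material exists, so its cost cannot be judged from them.

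### Allocation concealment is not described although one coordinator role both screens by hand and fits the inserts, and Kellgren-Lawrence grade is not named in the GEE model

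*Combined protocol and SAP*

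**What the plan says.** **Assignment.** It is described twice. Methods has it done "through a random table generator application which will be coordinated through the TRIA Orthopaedic Center". Study Procedures (Patient related) says patients are "randomized via a random table generated computer program to the wedge inserts or the flat inserts". Neither place gives an allocation ratio, blocks, strata, a concealment method or a holder of the list, and no other section supplies them. The reference to a stratified population under Significance concerns which patients are selected, not how they are allocated.

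**Screening.** Study Procedures states: "They will be screened for adequate knee laxity and subtalar motion before enrollment at each site". The training paragraph that follows Tailoring the Insole covers "training of the research coordinator for patient screening for adequate knee medial laxity and subtalar motion as well as proper fitting of the inserts". That paragraph also trains the site investigator in screening and consent.

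**Fitting.** Under Tailoring the Insole, the study coordinator will "perform the fitting of the test and control inserts based on patient randomization". The Insoles section makes the arms easy to tell apart: "The control insole is blue in color with a thin felt cover", level at 3 mm, while the wedge is green and rises from 3 mm to 10 mm.

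**Severity.** Inclusion Criteria require "symptomatic medial compartment knee osteoarthritis and Grade 2-4 Kellgren-Lawrence radiographic changes". The statistical analysis plan estimates WOMAC differences by GEE and treats secondary outcomes, radiographs among them, similarly. It names no baseline covariate for that model. The later Statistical Analysis paragraph names medication use and insert wearing time for regression, but not grade.

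**The concern.** There are two separate issues.

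**Concealment.** Some eligibility decisions are matters of judgement: medial laxity, subtalar motion and toe-box space. Toe-box space is the most exposed, because the question is whether the insole fits the shoe and the two insoles differ in thickness by up to 7 mm (10 − 3). A screener who knew the next assignment could pass a shoe for one insert and fail it for the other. Comparisons between arms would then be biased at entry, and no analysis could reliably undo it. The blinding of the statistician and radiologists acts after allocation and does not guard against this.

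**Severity.** Grade is a plausible predictor of outcome, above all for joint space, since the rationale for inclusion links end-stage lesions to potential for cartilage restoration. With 80 patients, a chance difference in grade between arms is quite likely. A model without grade leaves that noise in the estimate, and the trial's stated purpose is to supply an effect size and power for a later trial.

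**Working it through.** The plan gives no SD, power or dropout, so the figure of 80 cannot be re-derived; it is not in dispute here.

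**Inputs.** From the documents: N = 80; grades 2 to 4; grade not named in the GEE. Assumed: simple 1:1 randomisation; 27 of 80 patients (about one third) in grade 4, with 20% and 50% as the range; an outcome difference of 0.5 SD between grade 4 and the rest.

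**1. Chance imbalance in grade 4 share.** Let a ~ Binomial(27, ½) be the grade 4 patients and b ~ Binomial(53, ½) the others in the wedge arm. The difference in share is |a/(a+b) − (27−a)/(80−a−b)|. Summing the exact probabilities, with the same method for the other shares:

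| Grade 4 patients | ≥10 points | ≥15 points | ≥20 points |
|---|---|---|---|
| 16 (20%) | 0.29 | 0.11 | 0.03 |
| 27 (about one third) | 0.35 | 0.16 | 0.06 |
| 40 (50%) | 0.43 | 0.22 | 0.09 |

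**2. Effect on the contrast.** Shift = imbalance × outcome difference = 0.15 × 0.5 = 0.075 SD. The SE of an unadjusted difference at one time point with 40 per arm is √(2/40) = 0.224 SD. The shift is 0.075/0.224 = 0.34 of one SE.

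**3. Gain from adjustment.** The share of variance explained by grade is d²p(1−p) = 0.25 × 0.3375 × 0.6625 = 0.056. The SE is multiplied by √(1 − 0.056) = 0.972, a cut of about 3%. With d = 0.3 the cut is 1%; with d = 0.8 it is 7%.

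**4. Unequal arms.** P(48:32 or worse) = 2 × P(Binomial(80, ½) ≥ 48) = 0.093. The SE then becomes √(1/48 + 1/32) = 0.228 against 0.224, about 2% larger.

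**5. Predictability of the next arm.** Under simple randomisation, someone who has seen all earlier assignments still guesses the next correctly 50% of the time. Simulation of two grade strata (53 and 27 patients), always guessing the arm that is behind in the stratum, gave 70% correct with blocks of 4 and 69% with mixed blocks of 4 and 6. Blocks of 4 within grade strata do hold the grade gap to 5 points or less, so stratified blocking trades balance against predictability.

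**6. Concealment.** No arithmetic applies. Screening precedes enrolment, but that order alone does not hide the next assignment. Fitting shows the coordinator past and current arms, but not the next one unless the list is visible. Whether it is visible is the fact that the documents leave out.

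**The case against.** A reader might infer that assignments are open to foreknowledge. The documents do not say so. A computer application may well conceal them, coordination through the centre does not mean that the coordinator sees the table, and the site investigator is also trained in screening. Fitting takes place after assignment and reveals nothing about the next arm if randomisation is simple. All of this stands: the most that can be said is that no concealment is described.

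A reader might also infer that severity imbalance biases the result, or that the trial must stratify. Neither follows. Chance imbalance is not bias in expectation, and the usual standard error already allows for it. The gain from adjustment is small, and both the grade mix and the 0.5 SD are assumptions. The only effect sized is on WOMAC, whereas the stronger reason to expect grade to matter concerns joint space, a secondary outcome. Stratified blocks would add predictability where an unblinded coordinator screens and fits.

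Finally, this is a pilot, and the handling of BMI, activity and comorbidity is left to the later trial. That argues for cheap measures only. It does not excuse silence on concealment, because a pilot effect size distorted by selective enrolment would carry into the next trial's design.

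**Conclusion.** The point holds in two limited parts.

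- **Concealment is not described**, while one role is trained both for hand-judged screening and for fitting distinguishable inserts. The resulting selection bias is possible, not shown, and cannot be sized from the documents.
- **Grade is known for every patient but not named in the GEE.** A gap of at least 15 points in grade 4 share arises in 16% of trials (11% to 22% as the grade 4 share runs from 20% to 50%), assuming simple 1:1 randomisation. Under a 0.5 SD grade effect, such a gap moves the estimate by about a third of an SE, and adjustment cuts the SE by about 3%. This is lost precision, not bias.

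Concealment is the more important part, because a failure there could not be reliably repaired in the analysis.

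**What to change.** **In Methods, where randomisation is described:** state that the person who screens cannot view the list, and that the application releases each assignment only after the eligibility form (laxity, subtalar motion, toe-box space and grade) has been completed and locked. Name the role that holds the list. Study Procedures speaks of each site while Methods names one centre; if there is more than one site, say how this works at each.

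**In the statistical analysis plan:** add baseline Kellgren-Lawrence grade, with its coding fixed in advance, as a covariate in the GEE for WOMAC and in the joint-space analysis.

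**Optional:** stratified permuted blocks. They are not part of the required change. If they are used, the plan should acknowledge the higher predictability shown above.

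**Cost:** a few sentences, a setting in the application and one covariate; no extra patients or visits. Grade must be read before assignment, which eligibility already requires. The documents do not show whether someone who neither screens nor fits is available to hold the list, so the sponsor should confirm this.
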